12.11 Prohibited Therapies

The use of the following therapies will not be permitted:

- PPIs during the 10 days prior to screening and throughout the study.
- Prokinetics or H2 antagonists during the 5 days prior to screening and throughout the study.
- Systemic glucocorticosteroids or non-steroidal anti-inflammatory drugs (NSAIDs except low dose aspirin given for cardioprotection) on more than 3 consecutive days in the 28 days prior to screening and are not allowed throughout the study.
- PPI-based triple or quadruple therapy for eradication of H-pylori during the 28 days prior to screening and throughout the study.
- Mucous membrane protection drugs for 5 days prior to screening and throughout the study.
- Patients who have taken anti-cholinesterase drugs, traditional Chinese medicines for treating gastrointestinal disease, ulcerimin or misoprostol preparations within 7 days prior to screening or throughout the study.
- Macrolide antibiotics, such as erythromycin, azithromycin, from the day before screening and throughout the study.
- Any antacids within 24 hours before randomisation (Visit 2) and throughout the remainder of the study. Compound Sodium Alginate Double Action Chewable Tablets will be provided for symptom relief at the end of Visit 2 but must be stopped 24 hours prior to Visit 3.

Patients who use any of these above medications during the study will be withdrawn.

The Investigator Brochure indicates that due to the presence of calcium carbonate which acts as an antacid, a time-interval of 2 hours should be considered between Compound Sodium Alginate Double Action Chewable Tablet intake and the administration of other medicinal products, especially H2-antihistaminics, tetracyclines, digoxine, fluoroquinolone, iron salt, ketoconazole, neuroleptics, thyroxine, penicilamine, beta-blockers (atenolol, metoprolol, propranolol), glucocorticoid, chloroquine and diphosphonates.

13 SAFETY ASSESSMENTS

13.1 Adverse Events

13.1.1 Adverse Event Definitions

Adverse Event (AE): Any untoward medical occurrence in a patient participating in a clinical study administered an IMP, which does not necessarily have a causal relationship with administration of the IMP.

Comment: An AE can therefore be any unfavourable and unintended sign (including an abnormal laboratory finding), symptom, or disease temporally associated with the use of an IMP, whether or not considered related to the IMP.

AEs do not include the following:

- Medical or surgical procedures; the condition requiring a medical or surgical procedure is an AE.
- Elective surgery or pre-existing conditions requiring planned procedures outside the scope of the study.

Adverse Reaction (AR) to an IMP: All untoward and unintended responses to an IMP related to any dose administered.

Comment: All AEs judged by either the Investigator or the sponsor as having a reasonable causal relationship to an IMP qualify as ARs. The expression "reasonable causal relationship" means to convey in general that there is evidence or argument to suggest a causal relationship.

Serious Adverse Event (SAE): Any untoward medical occurrence (i.e. AE) that at any dose:

- Results in death.
- Is life-threatening.
- Requires hospitalisation or prolongation of existing hospitalisation.
- Results in persistent or significant disability/incapacity.
- Is a congenital anomaly/birth defect.
- Is otherwise considered to be medically significant.

Comments: Life-threatening in the definition of an SAE or serious AE refers to an event in which the patient was at risk of death at the time of the event; it does not refer to an event which hypothetically might have caused death if it were more severe.

Medical judgement should be exercised in deciding whether an AE or AR is otherwise considered to be medically significant. Important AEs or ARs that are not immediately life-threatening or do not result in death or hospitalisation but may jeopardise the patient or may require intervention to prevent 1 of the other outcomes listed in the definition above should also be considered serious.

Examples of such medically significant events are:

- Intensive treatment in an emergency room or at home for allergic bronchospasm.
- Blood dyscrasias or convulsions that do not result in hospitalisation.
- Development of drug dependency or drug abuse.

Unexpected Adverse Reaction: An AR, the nature or intensity of which is not consistent with the applicable product information (e.g. Investigator Brochure for an unauthorised IMP or SmPC for an authorised IMP).

Comment: When the outcome of the AR is not consistent with the applicable product information this AR should be considered as unexpected.

Suspected Unexpected Serious Adverse Reaction (SUSAR): An SAE considered to have a causal relationship with administration of the IMP, and the nature or intensity of which is not consistent with the applicable product information (e.g. Investigator brochure for an unauthorised IMP or SmPC for an authorised IMP).

Intensity: The term “severe” is often used to describe the intensity (severity) of a specific event. This is not the same as “serious”, which is based on patient/event outcome or action criteria.

13.1.2 Observation Period for Adverse Event Reporting

The observation period for an individual patient will start after giving informed consent and will finish at the last visit defining the end of the study for the given individual patient.

Any SAEs occurring after Informed Consent must be reported.

Any untoward medical events occurring after Informed Consent but prior to IMP administration should be recorded in the patient’s medical history and not reported as an AE.

13.1.3 Information to be Collected on Adverse Events

Each AE will be recorded according to the criteria given below. “Relationship to IMP” must be determined by the Investigator (if medically qualified) or by a medically qualified Co-Investigator.

Table 13-1 Table of Information to be Collected on Adverse Events

Variable	Category	Definition
AE reported term		Any untoward medical occurrence in a patient administered an IMP and which does not necessarily have to have a causal relationship with this treatment. An AE can therefore be any unfavourable and unintended sign (including an abnormal laboratory finding, for example), symptom, or disease temporally associated with the use of a medicinal product, whether or not considered related to the IMP.
Date AE started		The date on which the AE started.
Date of change in severity of AE		The date on which the AE changed in severity. This date equates to the finish date of the old severity and the onset date of the new severity.
Intensity	Mild Moderate Severe	Intensity will be determined by the Investigator. For symptomatic AEs the following definitions will be applied, but medical experience and judgement should also be used in the assessment of intensity. The AE does not limit usual activities; the patient may experience slight discomfort. The AE results in some limitation of usual activities; the patient may experience significant discomfort. The AE results in an inability to carry out usual activities; the patient may experience intolerable discomfort or pain.
Actions taken	None IMP dose changed IMP permanently discontinued Symptomatic therapy Patient hospitalised or hospitalisation prolonged Other action (specify)	No action was taken in relation to this AE. The dose of IMP was changed due to this AE, i.e. increase, decrease, or temporary discontinuation. The IMP was permanently discontinued due to this AE. Symptomatic therapy was added or changed due to this AE. The patient was hospitalised or hospitalisation was prolonged due to this AE. Other action was taken due to this AE, e.g. diagnostic tests, laboratories and procedures.
Relationship to IMP	Unassessable/ Unclassifiable	Insufficient information to be able to make an assessment.

Variable	Category	Definition
	Conditional/ Unclassified	Insufficient information to make an assessment at present (causality is conditional on additional information).
	Unrelated	No possibility that the AE was caused by the IMP.
	Unlikely	Slight, but remote, chance that the AE was caused by the IMP, but the balance of judgment is that it was most likely not due to the IMP.
	Possible	Reasonable suspicion that the AE was caused by the IMP.
	Probable	Most likely that the AE was caused by the IMP.
	Certain	The AE was definitely caused by the IMP.
Is the AE serious?	Results in death Life-threatening Requires or prolongs hospitalisation Results in persistent or significant disability/incapacity Congenital anomaly/birth defect Otherwise considered to be medically significant	See Section 13.1.1.
Date resolved		The date on which the AE ceased to be present.
Outcome	Not recovered/not resolved Recovered/resolved Recovered/resolved with sequelae Recovering/resolving Fatal Unknown	The AE still persists. The AE is resolved. The patient is stabilised, but with sequelae from this AE. The patient is recovering from this AE/this AE is resolving. The patient died whilst this AE was ongoing or as a result of it. The outcome of this AE is not known.
Has the patient ever experienced this AE before?	Yes/No	A query confirming whether the patient has a previous medical history of the AE at any time before entering into the study. If the patient has experienced this AE before, brief details should be given under additional information.
Additional information		Additional information regarding the AE.

13.1.4 **Procedure for Reporting Adverse Events**

All AEs that arise after the patient has had IMP administered will be recorded in the patient's CRF. AEs can be reported spontaneously by the patient or in response to non-leading questioning or observation by the Investigator, or be a significant laboratory abnormality.

The Investigator will ask the patient: "Are you experiencing any symptoms or complaints?" at the baseline visit and "Have you had any symptoms or complaints since the last visit?" during the study.

Assessments of the relationship of AEs to IMP must be made by the Investigator (if medically qualified) or by a medically qualified Co-Investigator.

13.1.5 **Procedure for Reporting Serious Adverse Events**

In the event of a Serious Adverse Event (SAE), the Investigator should telephone the Clinical Project Manager (CPM) within 24 hours of knowledge of the event. The name and contact number of the CPM will be provided to the Investigator in the study protocol and/or at the Study Initiation Visit. To allow timelines to be met the Investigator can report the event to the Global Vigilance Group (GVG) simultaneously by contacting GVG by email: [REDACTED]. The CPM will also forward any SAE information/forms to the RB Global Vigilance Group within the same day using the email address: [REDACTED]

Out of hours emergency contacts will be provided to the Investigator in the study protocol and/or at the Study Initiation Visit. If notification is via telephone the CPM will ensure that a SAE Form is completed but the Investigator will be requested to make a detailed written report by sending a follow-up SAE Form as soon as possible. The CPM will be responsible for reporting the event to the Global Vigilance Group ([REDACTED]). All the SAE forms will be provided to the CPM function via email, and a copy filed in the TMF. Any inconsistencies in the information received from the Investigator will be clarified using the Adverse Event Data Clarification Form.

If the case does require reporting, a CIOMS (Council for International Organizations of Medical Sciences) form will be produced. A copy of this will be sent to the RB Drug Safety Officer (DSO) in China who will complete the SFDA SAE Form in Chinese and submit to the SFDA within 7 days for fatal or life-threatening events, or 15 days for all events.

[figure not shown]
If the event requires expedited reporting (event classified as a SAE):

1. The IEC/IRB, SFDA and PFDA will be notified by the Investigator within 24 hours of awareness
2. All other investigators participating in the study will be informed by the CPM

The Investigator will be instructed to retain a copy of all the SAE Forms in the Investigator Site File, and must inform his/her local ethics committee/institutional review board of all SAEs occurring in the study.

The Investigator should not break the randomisation code except when it is necessary to do so in order to ensure the patient receives appropriate medical care (see Section 12.2).

The overall procedure for reporting SAEs is illustrated in the flowchart below.

Figure 13-1 Procedure for Reporting SAEs

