16.2 ADVERSE EVENTS

Adverse Events (AEs) will be coded using MedDRA version 16.0. For an individual patient, only adverse events commencing after first dose of IMP and no later than last dose of IMP+1day will be included in the AE and serious adverse event (SAE) summaries. AEs that began prior to the first dose of IMP or more than one day after the final dose of IMP will not be included in the analysis. Where an AE start date is partially or completely missing, and it is unclear using partial dates as to whether the AE is treatment-emergent, it will be assumed that it is.

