16.2.4 ADVERSE EVENTS LEADING TO DEATH

AEs leading to Death are those events with outcome reported as "Fatal" in the Adverse Events page of the CRF. A summary of AEs leading to death by SOC and PT will be prepared. This information will also be listed.

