16.3 DEATH

As only AEs leading to death are recorded for this study, please refer to Section 16.1.4.

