- 14.3.2.4 Overall Related Serious Adverse Events by System Organ Class, Preferred Term and Intensity – Safety Population
- 14.3.2.5 Adverse Events during the 4-hour Post Dosing Period by System Organ Class, Preferred Term and Intensity – Safety Population
- 14.3.2.6 Related Adverse Events during the 4-hour Post Dosing Period by System Organ Class, Preferred Term and Intensity – Safety Population
- 14.3.2.7 Serious Adverse Events during the 4-hour Post Dosing Period by System Organ Class, Preferred Term and Intensity – Safety Population
- 14.3.2.8 Related Serious Adverse Events during the 4-hour Post Dosing Period by System Organ Class, Preferred Term and Intensity – Safety Population
- 14.3.2.9 Adverse Events Leading to Dose Change by System Organ Class and Preferred Term – Safety Population
- 14.3.2.10 Adverse Events Leading to Study Discontinuation by System Organ Class and Preferred Term – Safety Population
- 14.3.2.11 Adverse Events Leading to Death - Safety Population
- 14.3.2.12 Serious Adverse Events Leading to Dose Change by System Organ Class and Preferred Term – Safety Population
- 14.3.2.13 Serious Adverse Events Leading to Study Discontinuation – Safety Population

- 14.3.3.1 Hematology: Observed Values – Safety Population
- 14.3.3.2 Hematology: Change from Baseline at Visit 3 – Safety Population
- 14.3.3.3 Clinical Chemistry: Observed Values – Safety Population
- 14.3.3.4 Clinical Chemistry: Change from Baseline at Visit 3 – Safety Population

Document: Reckitt Benckiser GA1202 Statistical Analysis Plan

Author:

Version Number:

Final 5.1

Version Date:

[25Feb2014]

Template No: CS_TP_BS016 – Revision 3

Reference: CS_WI_BS005

Effective Date: 01May2012

Page 24 of 29

- 14.3.3.5 Abnormal Results in Hematology – Safety Population
- 14.3.3.6 Abnormal Results in Clinical Chemistry – Safety Population
- 14.3.3.7 Clinically Significant Results in Hematology – Safety Population
- 14.3.3.8 Clinically Significant Results in Clinical Chemistry – Safety Population
- 14.3.3.9 Shift Table for Hematology – Safety Population
- 14.3.3.10 Shift Table for Clinical Chemistry – Safety Population

- 14.3.4.1 Vital Signs: Observed Values – Safety Population
- 14.3.4.2 Vital Signs: Change from Baseline at Visit 3 – Safety Population
- 14.3.5.1 Summary of Physical Examination Results – Safety Population
- 14.3.5.2 Shift Table for Physical Examination – Safety Population

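### AEs that were only ongoing at death are coded Fatal and would then be tabulated as AEs leading to death

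*Protocol*

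**What the plan says.** Protocol 13.1.3, Table 13-1, lists six AE outcomes with six definitions in the same order. The fifth, Fatal, is defined as: "The patient died whilst this AE was ongoing or as a result of it". The first, Not recovered/not resolved, means that the AE persists. The same table separately records why an AE is serious, in a list of criteria that begins "Results in death Life-threatening Requires or prolongs hospitalisation".

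SAP 16.2.4 builds the death output on the outcome field: "AEs leading to Death are those events with outcome reported as" Fatal on the AE page of the CRF. It continues: "A summary of AEs leading to death by SOC and PT will be prepared", and says that the data will also be listed. The outputs are "14.3.2.11 Adverse Events Leading to Death - Safety Population" and Listing 16.2.5.9 (Death). SAP 16.3 has no analysis of its own and refers back to the AE section, with the reason "As only AEs leading to death are recorded for this study". (It cites Section 16.1.4; the section meant is numbered 16.2.4.)

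SAP 16.2 limits the AE and SAE summaries by onset: "only adverse events commencing after first dose of IMP and no later than last dose of IMP+1day will be included".

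Death is also one of the reasons for withdrawal in Protocol 11.7.1 and for early termination in Protocol 11.3.2.3. SAP 9 summarises withdrawal reasons by treatment sequence group and overall (Table 14.1.1) and lists completion and withdrawal information (Listing 16.2.1.1).

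**The concern.** The table title makes a causal claim that the data item behind it does not carry. The two limbs of the Fatal definition are joined by 'or', so the first is enough alone: an AE that played no part in a death, but had not resolved when it happened, is coded Fatal. The SAP then presents it as an AE that led to the death. A mild throat irritation still present when a patient died of something else would qualify.

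At stake is the accuracy of the most serious safety table. Which AEs are said to have led to a death could be wrong, and their number could be too high. Because an AE ongoing at death also fits Not recovered/not resolved, two sites could code the same case differently, and the table would then depend on coding habit.

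**Working it through.** The plan gives no figure to reproduce, so the check follows the definitions in order.

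1. **Coding.** Suppose a patient dies of event A while AE B, which did not contribute, is ongoing. A meets the second limb of the Fatal definition (the patient died as a result of it). B meets the first limb (the patient died while it was ongoing). Both may be coded Fatal. B also fits Not recovered/not resolved, and Table 13-1 does not say which code takes precedence.

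2. **Derivation.** SAP 16.2.4 selects on outcome = Fatal and nothing else. A and B are both selected as leading to death.

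3. **Other filters.** The only further restriction is the onset window in SAP 16.2, from after the first IMP dose to the last IMP dose plus one day. It is a rule about timing and cannot separate A from B by cause. It is stated for the summaries and the analysis; the SAP does not say whether Listing 16.2.5.9 is cut to it.

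4. **Count.** With one causal event and k other in-window AEs ongoing at the death:
   - AEs shown as leading to death = k + 1
   - AEs that did lead to death = 1
   - For an assumed k = 2: 2 + 1 = 3 shown, against 1. For k = 0 there is no error.
   - Patients who died = 1, whatever k is.

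   The table templates mentioned in SAP 8 are not in the documents, so it cannot be seen whether Table 14.3.2.11 counts events or patients. In either case B would have a row in a summary by SOC and PT.

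5. **Exposure to the problem.** Planned enrolment is 44 (Protocol 14.1). Visit 3 falls 7 ± 2 days after Visit 2, so the onset window for a completing patient is at most 9 + 1 = 10 days. The 19-day maximum participation is that same 9 days plus up to 10 days of screening (9 + 10 = 19), and the screening days lie outside the window. Patients are aged 18 to 65, severe disease of other major body systems is an exclusion, and Protocol 6 considers the risks low.

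6. **A causal field.** Results in death is one of the seriousness criteria in Table 13-1. It would select A and leave out B. SAP 16.2.4 does not refer to it.

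**The case against.** Four points can be made on the other side.

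**Deaths are reported elsewhere.** From SAP 16.3 a reader might infer that the AE-based output is the trial's only account of deaths. The documents do not support that. A patient who dies before completing is counted under withdrawal reasons in SAP 9, whatever the AE coding, provided that the site enters death and not AE as the primary reason. This stands, but it counts patients and does not correct which AEs are said to have led to the death. A death after completion would not be caught there.

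**A reader could detect the error.** SAEs are tabulated and listed, and all AEs are listed individually. A mild, non-serious AE would be missing from the SAE outputs, and with 44 patients one death is easy to trace. This also stands. It limits the harm but leaves the table title wrong.

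**The inclusive code is cautious.** It spares the investigator from deciding which of several ongoing events caused a death. A narrower code could omit a contributing event, so the change has a downside. That is a good reason to keep such events visible, but not to label them all as leading to death.

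**The replacement field may not be available.** The CRF is not in the documents, and SAP 16.2.3 uses only the record that an event was serious. Table 13-1 lists the criterion, but whether it reaches the analysis dataset as a separate variable cannot be confirmed.

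**Conclusion.** Wrong as written, minor. Followed literally, Protocol Table 13-1 and SAP 16.2.4 allow an AE that was only ongoing at death to be tabulated and listed as leading to it. The excess is k AEs for a death with k other in-window AEs ongoing.

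A reader might go further and infer that unrelated AEs will be reported as causes of death. The documents do not support that as a statement of fact. It takes a death, another AE unresolved at that moment, onset of that AE inside the window, and a site that codes it Fatal and not Not recovered/not resolved. A death is unlikely in 44 patients over so short a window, and the number of patients who died would not be inflated. No efficacy result depends on this.

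Here, unrelated means unrelated to the death. Relationship to IMP is a separate field and is not in question. The conclusion assumes that sites code as Table 13-1 is worded and that no CRF completion instruction outside these documents narrows the Fatal code.

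**What to change.** - **SAP 16.2.4:** derive AEs leading to death from the seriousness criterion Results in death. Keep AEs that were only ongoing at death in the listing, labelled as such. Keep events of uncertain contribution in the table, so that the narrower definition does not hide them.
- **If that criterion is not a separate variable in the data:** leave the derivation as it is and retitle Table 14.3.2.11 and its listing as AEs with fatal outcome (ongoing at or resulting in death).
- **Protocol Table 13-1:** align the Fatal wording with the chosen definition, and state how an AE ongoing at an unrelated death is coded, so that the overlap with Not recovered/not resolved is removed. If data collection is complete, the SAP change alone is enough.
- **SAP 16.3:** report the number of patients who died, including any death after study completion, which the withdrawal summary would miss. Correct the cross-reference to 16.2.4.

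The cost is a few lines in the SAP and one in the CRF instructions. No new data are needed if the seriousness criterion was captured as Table 13-1 lists it. The one real burden is the investigator's judgement of which event resulted in death.
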